1.8 Method

RayStation® is a flexible, innovative treatment planning system. It combines unique features like unmatched adaptive therapy capabilities, multi-criteria optimization,

optimization for HDR brachytherapy and external beam therapy with photons, electrons, protons as well as helium and carbon ions. RayStation supports a wide range of treatment machines, providing one control center to create biomechanical deformable registrations using “Morpheus”. Morpheus lets the investigators focus all their skill and experience on evaluating and refining plan quality.

To investigate the impact of the proposed biomechanical model on clinical decisions during ablation guidance and end-point assessment, patients will be randomized in two treatment arms (i.e. experimental arm - including anatomical modeling of the liver, and control arm) with a 1:1 ratio. The primary objective is to assess whether applying biomechanical models during percutaneous ablation will increase the minimal ablation margins, which will be evaluated at the end of the procedure with the proposed software on both cohorts. Additionally, two other distinct end-points will be analyzed: ability of the model to provide tumor identification for ablation probe placement on intra-procedural non-contrast enhanced CT, and local tumor control rates achieved with the clinical application of this model. Operating physicians will be informed in respect which arm the patient was randomized at the time of ablation (figure 3).

[figure not shown]

Figure 3: Patient randomization flowchart

A. Impact on tumor targeting

The clinical trial will be designed according to the optimized parameters from our retrospective analysis. The optimized biomechanical models will be used to assess the accuracy (e.g. the ability of the model to accurately describe the motion, deformation, and volume change and tumor location in the liver between the pre-ablation contrast-enhanced CT and the intra-procedural non-contrast enhanced CT) in both cohort of patients. For the control arm, no information in respect tumor location and targeting will be provided for the operating physician during ablation. Imaging processing using the biomechanical model will be performed after procedure completion. For the experimental

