arm, tumor location and confirmation of appropriate targeting with ablation probe will be performed intra-procedurally utilizing the proposed software. Differences in tumor targeting accuracy between the two cohorts will be evaluated. If the accuracy of the cross validation cohort is not statistically significantly different, using a paired Student's T-test based on the preliminary retrospective results with significance defined as a p value of less than 0.05, from the initial optimization and validation results, then the model will be identified as complete. If the results are statistically worse, as an alternative approach, the initial cohort of patients will be used to perform an independent optimization of the model. Collaborations with the statistician will ensure that the appropriate power study has been performed for the analysis. The completion of this investigation will provide the accuracy of the present model in identifying and facilitate targeting of the liver tumors eligible for ablation when compared to the currently utilized standard of care tumor for tumor identification and targeting.

B. Impact on minimal ablation margins

A post ablation contrast-enhanced CT will be performed as per standard of care to assess the minimal ablation margins. Such assessment is currently performed manually using local rigid anatomic landmarks of the liver between the pre-ablation and post-ablation contrast-enhanced CTs. In this aim, we will evaluate the impact on the use of the advanced biomechanical model-based deformable alignment incorporating motion, deformation, and ablation-related volume loss in the liver between the pre-ablation contrast-enhanced CT and the post-ablation contrast-enhanced CT. The model will

automatically generate a minimal ablation margin on a three-dimensional Cartesian plan.

Such information will be utilized by the operator physician on the experimental arm to determine whether additional ablation is needed at a particular region surrounding the target tumor using a cut-off of at \geq 5 mm of minimal ablation margins in relation to the tumor borders in all planes (treatment arm). The \geq 5 mm minimal ablation margin will be used to account for the margin of error of the software, which is currently 3 mm. Frequency of total coverage of the target tumor, minimal ablation margins distance, and

[figure not shown]

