Figure 4: Image fusion of pre- and post-ablation contrast-enhanced CT using the proposed biomechanical model-based deformable image registration (Morfeus). Blue line: deep learning-based segmentation of the liver; Red line: gross-tumor volume (GTV) contouring; Green line: gross-ablation volume. A minimal ablation margin of < 5 mm was detected on the latero-posterior aspect of the GTV (arrow).

need for re-ablation between the two cohorts will be analyzed to identify the impact of this model on intra-procedural decision-making.

C. Impact on local tumor control

Rates of local recurrence following ablation in the most recent series varies from 20% to 45%. Although re-ablation on a different session is a feasible option in a minority of patients with recurrence at the ablated tumors, this incurs several disadvantages associated with the need to undergo another invasive procedure such as emotional stress, increased exposure to complications related to anesthesia and ablation procedure, radiation exposure, additional use of intravenous contrast media, and

increased associated costs. Given the complex volumetric and spatial changes of the liver post-ablation, the ability to map the previous treatment onto the new treatment plan is critical not only to avoid treatment related toxicities, but also to ensure that the patients receive adequate treatment with optimal coverage. We hypothesize that the use of this current model might improve local tumor control rates at 2-years follow-up. The completion of this aim will evaluate our hypothesis that the applied biomechanical model will improve local tumor control at 2-year when compared to the standard of care control arm.

Note: Final Analysis (n = 100 evaluable subjects)

Figure 5: Clinical Trial schema

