As a secondary objective, the Kaplan-Meier method will be used to estimate local tumor progression-free survival (LTPFS) and 95% confidence intervals for the quantiles of the LTPFS function based on the method of Brookmeyer and Crowley will be calculate for each arm. Time point probabilities (e.g., 2-year LTPFS) and the associated log-log transformed pointwise 95% confidence will also be reported. A multivariate Cox-proportional hazards model will be fitted to the data with ablative margin as a continuous variable to assess the significance of study arm and ablative margin size on LTPFS while simultaneously adjusting for known covariates that effect LTPFS. LTPFS will be measured from date of ablation to earliest date of progression at the ablated lesion, death. Those progression free and alive will be censored at their date of last clinic visit. Similar analysis will be used for 2-years intra-hepatic (progression at any site of the liver) progression-free survival and overall survival. Standard summary statistics will be computed for complication rates, quality of life, and liver function and compared between arms. Statistical significance will be defined as $p < 0.05$.

B. Randomization

A dynamic randomization method by Pocock and Simon will be used with a minimization probability parameter of 0.90. The randomization process will be controlled to ensure a balanced stratification by treatment arm for the factors listed above. Patients will be randomized to either experimental arm or no control arm using the Clinical Trial Conduct (CTC) website (<https://biostatistics.mdanderson.org/ClinicalTrialConduct>), which is housed on a secure server at MDACC and maintained by the MDACC Department of Biostatistics. Access to the website will be gained through usernames and passwords provided by the MDACC Department of Biostatistics to the clinical team. Training on the use of the CTC website to randomize patients on the study will be provided by the biostatistical collaborators. This is an open-label trial with stratified randomization. When a patient is enrolled on the study, the research nurse or coordinator of the study will enter patient's information including medical record number and stratification factors. Through the web interface, after the randomization button is clicked, the result of the randomization will be displayed on the screen for users to view. All data on randomization will be stored in a secure SQL server database.

PROTOCOL MONITORING PLAN

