We are interested in some things about you and your health. Please answer all of the questions yourself by circling the number that best applies to you. There are no "right" or "wrong" answers.

	Not at All	A Little	Quite a Bit	Very Much
1. Do you have any trouble doing strenuous activities, like carrying a heavy shopping bag or a suitcase?	1	2	3	4
2. Do you have any trouble taking a long walk?	1	2	3	4
3. Do you have any trouble taking a short walk outside of the house?	1	2	3	4
4. Do you need to stay in bed or a chair during the day?	1	2	3	4
5. Do you need help with eating, dressing, washing yourself or using the toilet?	1	2	3	4

During the past week:

	Not at All	A Little	Quite a Bit	Very Much
6. Were you limited in doing either your work or other daily activities?	1	2	3	4
7. Were you limited in pursuing your hobbies or other leisure time activities?	1	2	3	4
8. Were you short of breath?	1	2	3	4
9. Have you had pain?	1	2	3	4
10. Did you need to rest?	1	2	3	4
11. Have you had trouble sleeping?	1	2	3	4
12. Have you felt weak?	1	2	3	4
13. Have you lacked appetite?	1	2	3	4
14. Have you felt nauseated?	1	2	3	4
15. Have you vomited?	1	2	3	4
16. Have you been constipated?	1	2	3	4

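### The open-label declaration masks no one, although only the operating team and randomising staff need the arm; this leaves the QLQ-C30 comparison and the progression part of LTPFS open to avoidable bias

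*Combined protocol and SAP*

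**What the plan says.** Statistical Methods, part B (Randomization): "This is an open-label trial with stratified randomization". The same part says that a research nurse or coordinator enters the patient and that "the result of the randomization will be displayed on the screen for users to view". It sets no limit on passing the result on.

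Section 1.8 (Method): "Operating physicians will be informed in respect which arm the patient was randomized at the time of ablation". The reason is given under the heading on minimal ablation margins: "Such information will be utilized by the operator physician on the experimental arm to determine whether additional ablation is needed". For controls, under the heading on tumor targeting, "Imaging processing using the biomechanical model will be performed after procedure completion".

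Two of the planned secondary comparisons depend on a person's judgement:

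- **Quality of life.** Part A (Analysis Plan) says "Standard summary statistics will be computed for complication rates, quality of life, and liver function and compared between arms". The instrument is the EORTC QLQ-C30, which tells the patient "Please answer all of the questions yourself by circling the number that best applies to you".
- **LTPFS.** This is the first secondary objective in section 1.2. Section 1.8, part C, aims to test whether "the applied biomechanical model will improve local tumor control at 2-year when compared to the standard of care control arm". Part A counts progression at the treated site or death as the event, estimates the curve in each arm, and fits a Cox model that includes study arm. The table in section 1.9 lists follow-up CT as standard of care. No section says who makes the progression call, by what criteria, or whether that person may know the arm.

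**The concern.** An operator who must act on the software cannot be masked. That reason does not extend to the patient or to the reader of follow-up scans. In both arms the patient has a percutaneous ablation, the same CT time points and the same visits, and in controls the software is run only after the procedure.

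A patient who knows that software guided the ablation, or did not, may answer a self-completed questionnaire differently. A reader who knows the arm may lean one way on a doubtful finding at the ablation site. Either would put a difference between arms into secondary objectives 1 and 3 that the ablation did not cause, and analysis cannot reliably remove it once the scores and calls are recorded. Death cannot be affected in this way, so overall survival and the death component of LTPFS are outside this point. So is the primary margin measurement.

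**Working it through.** **1. Who needs the arm, by role**

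| Role | What the documents say | Needs the arm? |
|---|---|---|
| Operator | Told at ablation; acts on the margin in the experimental arm (1.8) | Yes |
| Randomising staff | See the result on screen (Statistical Methods, B) | Yes |
| Patient completing the QLQ-C30 | Nothing beyond open-label | No reason given |
| Person dating local progression | Role not described | No reason given |

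**2. The plan's own figure.** Number of Participants: 50 per arm, difference 1.132 mm, SD 2, two-sided 0.05. Noncentrality = 1.132 / (2 × √(2/50)) = 1.132 / 0.4 = 2.83. Exact t power with 98 df = 0.800. The stated 80% reproduces, so 50 per arm is used below. The plan states no power for LTPFS or quality of life.

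**3. Local control: assumed bias.** The documents give no rate of equivocal findings and no call rates, so these inputs are assumptions.

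False difference = share equivocal × difference in call rate between arms.

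- No dependence on arm: 0 points.
- 10% equivocal, called progression in 60% of controls and 40% of experimental patients: 0.10 × 0.20 = 2 points (1 patient in 50).
- 20% equivocal, 70% against 30%: 0.20 × 0.40 = 8 points (4 patients in 50).

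**4. Against sampling error.** Section 1.8, part C, cites local recurrence of 20% to 45%. SE of a difference = √(2p(1−p)/50).

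- p = 0.20: √(2 × 0.20 × 0.80 / 50) = 0.080.
- p = 0.45: √(2 × 0.45 × 0.55 / 50) = 0.0995.

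Two points is 2/9.95 to 2/8.0 = 0.20 to 0.25 SE. Eight points is 8/9.95 to 8/8.0 = 0.80 to 1.0 SE. With a shift of δ standard errors and no true effect, the chance of a two-sided p < 0.05 is Φ(−1.96 + δ) + Φ(−1.96 − δ): about 5% to 6% for 2 points, and about 13% (δ = 0.80) to 17% (δ = 1.0) for 8 points. This treats 2-year local control as a simple proportion and ignores censoring and death.

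**5. A different assumption.** Suppose instead that readers miss 10%, 20% or 30% of true progressions in the experimental arm only. Simulated with 50 per arm and no true difference, the false-positive rate goes from about 5% to 6%, 9% and 13% at a true rate of 20%, and from about 6% to 8%, 16% and 29% at 45%. The last figure corresponds to 0.45 × 0.30 = 13.5 points. Nothing in the documents suggests under-calling that strong, so it is not carried into the conclusion.

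**6. Quality of life.** With an assumed expectation shift of b SD, noncentrality = b / √(2/50) = b / 0.2. For b = 0.1, 0.2 and 0.3 this is 0.5, 1.0 and 1.5, and the false-positive rate is about 8%, 17% and 32% instead of 5%.

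**The case against.** Open-label is a stated choice for a device that the operator must use, and these outcomes are secondary. Several stronger readings are tempting, and the documents do not support them.

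- **That patients and CT readers are told the arm.** No section says so. It is an inference from an unqualified term and the absence of any masking rule. Consent pages are not available, so what patients are told cannot be checked. Access to the software is limited to authorised study investigators; that is a confidentiality control, but it means outside readers are not shown to have the margin.
- **That the protocol itself calls follow-up scans hard to read.** It does not. The remark on inflammation and volume loss in section 1.4 concerns assessment during the procedure and presents later imaging as the remedy. The remark on liver changes in section 1.8, part C, concerns mapping an earlier treatment onto a new plan.
- **That pain is a separately exposed endpoint.** The Numeric Pain Rating Scale is collected as standard of care but is not a named endpoint. Pain enters a planned comparison only through the QLQ-C30.
- **That the bias must favour the software.** That direction is plausible but assumed.

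It is also fair that CT at 45 days and 3, 6, 12 and 24 months gives later scans a chance to settle an early doubtful finding, so the false differences above may be too large. A line on the imaging request masks nobody if study investigators make the progression call. Withholding the software margin from clinical readers is debatable, and the fix does not ask for it. Finally, patients enrolled after a positive interim look all receive the experimental procedure and cannot be masked.

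What stands against all this is that no reason is given for the patient or the progression reader to know the arm, and no provision keeps it from them.

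**Conclusion.** The point holds for two secondary comparisons: the QLQ-C30 and the progression component of LTPFS. As written, the plan leaves both open to a bias that it could reduce at little cost.

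The size cannot be known from the documents. Under the equivocal-finding assumptions it lies between nothing and about 8 points in 2-year local control, at most about one standard error with 50 randomised patients per arm. If calls and answers do not depend on the arm, there is no bias. A reader might infer that the LTPFS or quality-of-life results will be invalid; the text does not support that. It supports a cheap improvement.

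**What to change.** In Statistical Methods, part B, replace the open-label sentence with text to this effect:

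- The operating team and the randomising staff know the arm.
- Randomised patients are not told their arm until they have completed their last QLQ-C30.
- The arm is left off follow-up CT requests.
- The LTPFS progression date is taken from the existing standard-of-care read by a radiologist who was not the operator and was not told the arm.
- Patients enrolled to the experimental arm only, after a positive interim look, are exempt and are kept out of the randomised comparison of these outcomes.

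The cost is protocol and consent wording and a rule for imaging requests, with no extra scans or reads. The downsides are some leakage through the procedure note and delayed disclosure to patients. The sponsor would first have to establish who reads the follow-up scans, since the protocol does not say.

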We are interested in some things about you and your health. Please answer all of the questions yourself by circling the number that best applies to you. There are no "right" or "wrong" answers.

	Not at All	A Little	Quite a Bit	Very Much
1. Do you have any trouble doing strenuous activities, like carrying a heavy shopping bag or a suitcase?	1	2	3	4
2. Do you have any trouble taking a long walk?	1	2	3	4
3. Do you have any trouble taking a short walk outside of the house?	1	2	3	4
4. Do you need to stay in bed or a chair during the day?	1	2	3	4
5. Do you need help with eating, dressing, washing yourself or using the toilet?	1	2	3	4

During the past week:

	Not at All	A Little	Quite a Bit	Very Much
6. Were you limited in doing either your work or other daily activities?	1	2	3	4
7. Were you limited in pursuing your hobbies or other leisure time activities?	1	2	3	4
8. Were you short of breath?	1	2	3	4
9. Have you had pain?	1	2	3	4
10. Did you need to rest?	1	2	3	4
11. Have you had trouble sleeping?	1	2	3	4
12. Have you felt weak?	1	2	3	4
13. Have you lacked appetite?	1	2	3	4
14. Have you felt nauseated?	1	2	3	4
15. Have you vomited?	1	2	3	4
16. Have you been constipated?	1	2	3	4
